In an initial pilot study the CF-BS-ETEC vaccine was shown to confer 82% protective efficacy ($p < 0.05$) against ETEC disease in European travelers going to 20 different countries in Africa, Asia and Latin America (Wiedermann *et al.* 2000). However, the number of cases fulfilling the inclusion criteria was low. In a large placebo controlled trial in nearly 700 American travelers going to Mexico and Guatemala the ETEC vaccine was shown to be effective (protective efficacy 77%) against non-mild ETEC diarrheal illness, i.e. disease that interfered with the travelers' daily activities (Sack D.A *et al.* 2002, Svennerholm and Savarino 2004). However, in a recent pediatric study in rural Egypt the vaccine did not confer significant protection in the 6-18 months old children tested (Savarino *et al.*, to be published).

There are a number of factors that may explain why enteric vaccines have lower efficacies in children in developing countries than in older children and adults in developed as well as in developing countries (Clemens *et al.* 1985, Richie *et al.* 2000, Savarino *et al.* 2004). Pre-existing malnutrition can lead to more severe enteric infections, possibly due to the immunocompromised nature of the host that also predisposes individual to greater bacterial load in the mucosal surfaces of the gut than the well nourished child (Mathur R *et al.* 1985). In a study in India, diarrhoeal illness including that caused by ETEC was found to be more severe in children with malnutrition. These factors may also be the reason for the poor efficacy of enteric vaccines in infants and young children.

Micronutrient deficiency such as vitamin A and zinc is quite common in developing countries and generally increases the morbidity due to diarrhoeal illnesses, although the effect on the morbidity of ETEC diarrhoea has not yet been studied (Rahman *et al.* 2001, Raqib *et al.* 2004). It has been estimated that in Bangladesh over 40% of children under 5 years of age may have zinc deficiency (Qadri *et al.* 2004). Supplementation with zinc increases the adaptive immune responses to cholera vaccination in children and adults (Albert *et al.* 2003, Qadri *et al.*, 2004, Karlsen *et al.* 2003) and in children with shigellosis (Raqib *et al.* 2004). The effect of micronutrient deficiency in the immune response in cholera and ETEC vaccine field has not been studied, but is an area that needs attention.

Principal Investigator: Last, first, middle [name]

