Based on this we plan to study three groups of children who will be given the cholera or ETEC vaccine formulated (A) in water (B) in bicarbonate-citric acid buffer (Recip AB, Stockholm) or (C) in a rice syrup based electrolyte buffer, CeraVacx (Cera Products Inc., Columbia, Maryland). One group in both vaccine groups will be given vaccine without any buffer, that is when dissolved in water. The best formulation will be used in further studies described below to study other interventions.

Sample size: Approximately children will be studied in each of three groups ($n=102 \times 3= 306$; $102 \times 3=306$).

Time frame: Within first 6 months of the initiation of the study.

2. Effect of breast feeding on vaccination

Breast fed infants aged between 6 month -2 years will be given the cholera and subsequently the ETEC vaccine. The children will be withheld from breast-feeding for a period of about 3 hours before ingestion of the vaccine and one hour after. In two weeks time a second dose will be given and the same protocol used. Age matched children will be allowed to breast feed within an hour of taking the oral vaccine. Only breast milk will be withheld and children will be allowed to drink

Age matched control children will be given breast milk without limitations.

Sample size- About 228 children will be studied ($57 \times 2=114$ for cholera vaccine; $57 \times 2=114$ for ETEC vaccine).

Principal Investigator: Last, first, middle [name]

Time frame: Within 6 months -2 years of the initiation of the study.

3. Effect of zinc on the immunogenicity of ETEC and cholera vaccine in young children

We would like to study the effect of zinc on the immunogenicity of oral cholera and ETEC vaccine.

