Baseline evaluation of samples:

Stool examination: A routine stool microscopic examination and culture for *V. cholerae* O1/O139 and ETEC will be carried out four days prior to vaccination. Children whose stools are positive for these pathogens will not be vaccinated since this will interfere in the evaluation of the response to the vaccine. When immunization for the second dose of the vaccine will be carried out (14 days after the first dose) children who have fever or diarrhoea will be excluded from the study.

Zinc: Serum zinc concentrations will be determined at baseline only. Venous blood collected in trace element free vacutainers will be placed in ice until arrival at the ICDDR,B laboratory on the same day. Serum will be assayed by flame atomic absorption spectrophotometry and zinc deficiency will be defined as a serum zinc concentration <60 ug/dl (31).

Vaccine, administration and allocation: Both the cholera and ETEC vaccine are produced by the Swedish Bacteriological Laboratories (SBL Vaccin AB Stockholm, Sweden). One dose of the ETEC vaccine contains 1.0 mg BS plus 2×10^{10} formalin inactivated bacteria each of 5 strains of ETEC expressing 6 colonization factors. The oral inactivated cholera vaccine (Dukoral) consists of killed bacteria prepared from individual batches of O1 El Tor and classical *V. cholerae* to include both LPS and protein antigens and also contains recombinant BS. One dose of vaccine contains 1.25×10^{11} CFU of the killed whole cell vaccine plus 1 mg of BS developed in Sweden and also produced by SBL. New batches of ETEC vaccine containing 1.0 mg of BS plus about 10^{11} formalin inactivated bacteria expressing colonization factors will be prepared for the study. For all children a quarter dose of the CF-BS-ETEC vaccine will be tested since some adverse events of vomiting was observed with the higher dose (Qadri et al. in manuscript).

Informed written consent will be taken from the parent/guardian for the children for the immunization and for the permission to draw blood and obtain stool samples (Appendices).

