Although the study is an open design, the clinician in the field will code the samples before sending them to the laboratory so that the laboratory personnel will be blinded when the analyses are carried out. The laboratory will only know if the samples have to be analyzed for the cholera or the ETEC vaccine immunological responses.

Samples from vaccines that will be collected at 3 time points will be tested for antibody responses. From blood PBMC will be separated for preparation of antibody in lymphocyte supernatants (ALS, Qadri et al. 2003). ALS and serum samples collected from vaccines at the preimmune (day 0) and post-vaccination days (day 7 and day 21) will be tested for antibody responses. ALS and sera from vaccinees receiving the CF-BS-ETEC vaccine or the cholera vaccine will be tested for the IgA antibody responses to different antigens including (for ETEC CFA/I, CS1,CS2,CS3,CS4,CS5, for cholera vaccine to LPS and to CTB for both). Using fecal extracts from the vaccinees at the 3 time-points, IgA antibody responses to CFA/I, V. cholerae O1 LPS and CTB will be measured. These procedures are already set-up in the laboratory of the investigators (Qadri et al. 2000,2003). Further to test the immunogenicity of the cholera vaccine we will test the vibriocidal antibody response at the 3 time points mentioned above as well as the response to LPS (O1 Ogawa and Inaba) using sera. In addition, the IgA and IgG antibody responses to rCTB will be measured in those being immunized with the cholera or the ETEC vaccine. The serum zinc level will also be assessed at the baseline in all the children since it may have an effect on the response to the intervention(s) and the vaccination.

Safety Monitoring Committee

[name] (CSD) will serve as the Chairperson of the committee. Other members include [name].(CSD), [name] (CSD) and [name] (LSD). The members are in no way involved with the project.

Safety endpoint and safety evaluation

The primary end point for evaluating safety will be defined as the occurrence of any of the following diarrhoea, vomiting or abdominal cramps of at least moderate grade. Diarrhea will be defined as three or more loose or liquid stools in any 24-h period. A measured oral or rectal temperature above 38°C will be considered a fever.

Overall laboratory tests for the project

Vaccinees:

Stools will be cultured on MacConkey agar and tested for colonization factors of ETEC by dot blot immunoassay

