The volunteers will be recruited from the urban slums in Mirpur in Dhaka for the study. The project office will be around the same area which is at present being used for other studies ongoing in ICDDR,B (projects: 98009, 99033, 2001-027,2000-027).

Clinical and field facilities:

The clinicians in the study will coordinate the clinical component of the study in the ICDDR,B hospital and in the Mirpur field site. Clinical facility needed in the study will be provided by the study physicians and other clinicians at the Clinical Research and Service Centre of the ICDDR,B hospital in Dhaka.

Laboratory facilities:

Existing laboratory facilities are adequate.

Data Analysis:

Methods to ensure data quality

All samples will be coded before reaching the laboratory and blinded until immunological analyses have been completed.

Data management; To maintain consistency the data forms will be reviewed by the investigators. This will be carried out to ensure the completeness and accuracy of the data. After editing, data will be entered in an appropriate data entry program that will be suitable for the study.

The data will be entered into a computer and a data base created. Data will be analyzed using an appropriate statistical programme, EpiInfo version 2000 or SPSS. Descriptive statistics will be generated using EpiInfo and SPSS for Windows (Version 10.00) or SigmaStat.

Statistical analysis will be carried out using appropriate parametric and non parametric tests. Overall rates of adverse reaction and seroconversion will be compared by χ^2 test with Yates correction or by the Fisher exact test. Seroconversion for the vibriocidal response will be defined as ≥ 4 fold rise in reciprocal serum vibriocidal titer from pre to post vaccination. If necessary, vibriocidal antibody titers will be transformed to logarithms to better approximate normality.

For the CF, LPS and CTB specific responses in ALS and serum samples, a ≥ 2 fold response from baseline to post vaccination will be considered a positive response. The increase in responses due to any intervention should be at least 2 fold or higher increase from that seen in the vaccinees in whom any intervention has not been carried out. We will therefore expect to see a 4 fold higher increase in the intervention group. Differences in the geometric mean titers (GMTs) of the antibody will be compared by the Mann-Whitney test or the Wilcoxon Rank Sum Test or the Student's t-test as found appropriate.

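### The breast-feeding control group is defined only by age matching in an open study, and no random assignment to withholding or control is described

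*Protocol*

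**What the plan says.** Protocol, section 2 (Effect of breast feeding on vaccination), has breast-fed children aged 6 months to 2 years go without breast milk for about 3 hours before and 1 hour after each of two doses. It describes the comparison group twice, in nearly adjacent sentences: "Age matched children will be allowed to breast feed within an hour of taking the oral vaccine" and "Age matched control children will be given breast milk without limitations". Neither sentence says how a child comes to be in one group or the other.

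The section that might be expected to say so opens: "Vaccine, administration and allocation: Both the cholera and ETEC vaccine are produced by the Swedish Bacteriological Laboratories". It goes on to vaccine content, dose, dissolving fluids and supplements, with no assignment rule. Under Coding of samples the protocol states: "Although the study is an open design, the clinician in the field will code the samples before sending them to the laboratory". The adverse event form in Appendix 5d carries a field for a random number, with no procedure attached to it.

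On feeding, Overall design for the vaccine studies repeats the 3 hours before and 1 hour after. It also sets a general one-hour fast on either side of every dose, with an exception only where a longer period is specified. Hypothesis 2 still gives 2 hours before the dose.

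**The concern.** The component asks a causal question: does withholding breast milk around the dose raise the response? That needs two groups that differ systematically only in the withholding. Matching on age makes them alike in age. It leaves open how often a child is breast fed, what enteric exposure the child has had, and the child's zinc status.

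The last of these is the protocol's own example. It says: "The serum zinc level will also be assessed at the baseline in all the children since it may have an effect on the response", and in the background: "It has been estimated that in Bangladesh over 40% of children under 5 years of age may have zinc deficiency". That second figure is a population prevalence. It shows that the factor is common enough to matter, not that the arms will differ on it.

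In an open study without a described assignment rule, field staff or families could influence which children have milk withheld. Willingness to withhold milk for some hours may itself go with how much the child depends on it. If the groups differ at entry for such reasons, a difference in response cannot be separated from them afterwards. Analysis can adjust for what is measured, such as zinc, but not for what is not.

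**Working it through.** **1. How many children are affected.** From the sample size paragraph and Appendix 2:
- Breast feeding: 57 per arm × 2 arms × 2 vaccines = 228
- Formulation: 102 × 3 × 2 = 612
- Zinc: 75 × 2 × 2 = 300
- Total: 612 + 228 + 300 = 1140, as stated; 228/1140 = 20.0%

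**2. The plan's own figure of 57 per arm.** Stated inputs are a one-sided test at about 95% confidence, a 55% response, a 50% relative improvement (0.55 × 1.5 = 82.5%) and 15% dropout. Power is not stated; 90% is assumed here. With p̄ = (0.55 + 0.825)/2 = 0.6875:

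n = [1.645·√(2 × 0.6875 × 0.3125) + 1.282·√(0.55 × 0.45 + 0.825 × 0.175)]² / 0.275² ≈ 46.8, so 47.

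Allowing for dropout, 47/0.85 = 55.3, so 56, close to the stated 57. The match is not unique: two-sided at 90% power without dropout gives 58. The size rests on a plain two-group comparison, so random assignment would leave it unchanged.

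**3. Where an assignment rule could stand.**
- Section 2 (breast feeding): age matching only.
- Vaccine, administration and allocation: no rule.
- Coding of samples: open in the field, coded for the laboratory.
- Appendix 5d: a random-number field, no procedure.
- Selection of study subjects: common eligibility and exclusions at one site, which narrow the population but do not assign children to arms.

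**4. The feeding rules.**
- Withholding arm: 3 + 1 hours in section 2 and in Overall design. Hypothesis 2 gives 2 + 1 hours. The ethics committee memorandum of 2 January 2005 (item c) asked for three hours instead of two, so the hypothesis line looks uncorrected.
- Controls: section 2 has one sentence on feeding within an hour of the vaccine and one on feeding without limit. Neither the general fast nor the withholding sentence in Overall design names the controls as exempt.

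**5. Illustration of what an entry imbalance can do.** The protocol gives no figure for imbalance, so these inputs are assumptions: no true effect, 55% response overall, a one-sided 5% test without continuity correction, and 48 evaluable per arm (57 × 0.85 = 48.45). A factor shifts response by 20 to 30 percentage points, and its prevalence differs by 10 to 30 points in the direction that favours withholding.

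Bias = shift × imbalance, from 0.20 × 0.10 = 2 points to 0.30 × 0.30 = 9 points.

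False-positive probability = Φ{[b − 1.645·√(2 × 0.55 × 0.45/48)] / √[(p₁q₁ + p₂q₂)/48]}, with p₁ and p₂ equal to 0.55 ∓ b/2 and q = 1 − p.
- b = 0.02: (0.020 − 0.167)/0.1015 = −1.45, giving 7.4%
- b = 0.09: (0.090 − 0.167)/0.1011 = −0.76, giving 22.3%

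With all 57 per arm evaluable the range is 7.6% to 24.8%. The Yates-corrected or exact tests named in the protocol are more conservative and would give lower values. An imbalance in the other direction would hide a real benefit instead. Chance imbalance under randomisation is already covered by the test's error rate; systematic imbalance is not.

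**The case against.** The strongest reply is that the text is silent rather than wrong. The random-number field points towards randomisation, the consent forms and some other pages are not available, and age matching can coexist with randomisation within age bands. All children come from one site and one age range, under the same exclusions (including recent zinc use and low weight for height), and the laboratory is blinded. Much of this stands. It rules out saying that assignment was non-random. It does not remove the point, because section 2 goes beyond silence: it names a basis for the control group, and a team following it as written would match on age and do nothing more.

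A reader might infer three stronger things that the documents do not support:

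- **That several feeding rules contradict the withholding period.** Only the 2 hours in hypothesis 2 does, and both operative sections agree on 3 + 1.
- **That the general fast binds the controls and shrinks the contrast.** The specific control sentences in section 2 largely answer this: they allow feeding within the hour and without limit. What remains is a missing exemption phrase.
- **That the named tests are at fault for ignoring the matching and baseline factors.** The protocol lists tests for rates ("test with Yates correction or by the Fisher exact test") and says titres "will be compared by the Mann-Whitney test or the Wilcoxon Rank Sum Test". Covariate adjustment is commonly left to a statistical analysis plan, which is not at hand, so nothing is counted here.

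Random assignment is likewise not described for the formulation and zinc groups. Those groups are not called age matched, so that is only missing detail.

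**Conclusion.** The point holds in a limited form and should be fixed. For 228 children, 20% of the total, the only described basis for the control group is age matching in an open study, so a difference between the arms could not be securely attributed to withholding breast milk. No size of bias is claimed: the protocol gives nothing from which to estimate it, and the illustrative range rests wholly on assumed shifts and imbalances. The conclusion rests on the available text. If a removed page describes randomisation, what remains is to bring section 2 into line with it. The feeding-rule inconsistencies are secondary and a matter of wording.

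**What to change.** In section 2 (Effect of breast feeding on vaccination), replace the age-matched wording with concurrent 1:1 randomisation of breast-fed children to withholding or no withholding, stratified by age, separately for each vaccine. Keep 57 per arm. If assignment is already random, say so there. The cost is a randomisation list, and the adverse event form already has a field for the number.

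Two wording changes go with it:
- Give one rule for controls: breast milk without limitation, expressly exempt from the one-hour fast in Overall design for the vaccine studies.
- Change 2 hours to 3 hours in hypothesis 2.

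As a clarification only, one sentence under Vaccine, administration and allocation could state how the formulation and zinc groups are assigned.

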Sequential progress of the vaccine studies: The vaccine studies will be carried out in a planned and organized manner as has been shown in Appendix 2. Some of the studies will be run in parallel. We hope that by doing this we will be able to maintain a smooth flow and momentum in the study and keep the committees aware of the progress and if necessary make changes as and when thought necessary. In addition this will help us analyze the data and make it available for dissemination, which will be helpful in progressing to Phase III studies of the different components.

Selection of study subjects for vaccine studies:

Healthy children (6 months to 2 years of age) both males and females who have not enrolled in any other research study including that are being conducted by ICDDR,B will be recruited from the urban slums of Mirpur.

Before entering into the study, subjects in the different age groups will be screened from the slums and history recorded and their consent to participate in the study will be obtained (Appendix 4a-4c). We have

previously observed that at least 60% of the families agree to participate in the study. The volunteers prior to enrollment in the study will be carefully examined by a physician. A detailed history of the volunteer of previous immunizations, nutritional status, recent illness (as outlined below) that can compromise the immune system, family background etc. will be taken (Appendix-4a-c). The volunteers should be free from any chronic disease or any recent illness that may compromise the immune system. Children will be excluded from enrollment if interviewers find: (a) a history of chronic gastrointestinal disorder, (b) diarrhoeal illness in the past 2 weeks (diarrhoea being defined as passing of ≥ 3 loose or liquid stools in 24 hours) (c) febrile illness in the preceding week, or (d) other serious chronic illness (e) had antibiotic treatment at least 7 days prior to the enrollment in the study (f) children suffering from third degree of protein energy malnutrition (PEM). The nutritional status of the children to be recruited for the vaccine studies will be monitored using anthropometrical measurements (weight-for-age, and weight-for-length/height). Children below -2SD for weight for height/length of the NCHS median will not be enrolled. Children who have received zinc in the past two months will also not be recruited.

We plan to recruit children in the 6 month -2 year range for immunization.

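### Antibiotic exclusion (e) points the wrong way: read literally, it bars children treated a week or more ago and does not itself bar those treated in the last few days

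*Protocol*

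**What the plan says.** In the Protocol, under the heading on selection of study subjects for vaccine studies, the list (a) to (f) opens with "Children will be excluded from enrollment if interviewers find". Every item is therefore a reason to keep a child out. Item (e) is "had antibiotic treatment at least 7 days prior to the enrollment in the study".

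Three other criteria in that section carry a time limit: (b) "diarrhoeal illness in the past 2 weeks", (c) "febrile illness in the preceding week", and, after the list, "Children who have received zinc in the past two months will also not be recruited".

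Under Baseline evaluation of samples, the stool examination comprises microscopy and culture, and the culture for V. cholerae O1/O139 and "ETEC will be carried out four days prior to vaccination". The consequence and its reason are given together: "Children whose stools are positive for these pathogens will not be vaccinated since this will interfere in the evaluation of the response to the vaccine".

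**The concern.** A phrase that would work as an inclusion condition (last antibiotic no sooner than a week ago) has been placed under an exclusion stem. This reverses its meaning. Item (e) is an operative eligibility rule that interviewers apply child by child, not background text.

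Two things are at stake. First, with no upper limit, the literal rule bars a child for any course taken 7 or more days earlier, however remote. That would narrow and alter the eligible population of 6- to 24-month-olds. Second, it leaves recent treatment unrestricted by (e). A child treated shortly before the stool culture might test negative while carrying or clearing one of the two pathogens, and the protocol wants carriers kept out so that the vaccine response can be evaluated.

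Because the components are recruited in sequence, staff could also read an ambiguous rule differently from one component to the next.

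**Working it through.** No figure in the plan depends on this rule, so there is nothing to recompute. The check is one of logic and of comparison between sections.

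**Step 1: literal direction of (e).** Let d be the number of days between the last antibiotic dose and enrolment, for a short course lying wholly at that point. The stem makes the condition an exclusion, and the wording sets d ≥ 7. The last column shows, for contrast, a one-week look-back (exclude if d ≤ 7). The one-week length is an illustrative assumption, not a statement of the right window.

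| d | (e) as written | one-week look-back (illustration) |
|---|---|---|
| 2 | not excluded | excluded |
| 6 | not excluded | excluded |
| 7 | excluded | excluded |
| 60 | excluded | not excluded |

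The two readings agree only at the boundary. A course that began 7 or more days ago and is still running arguably meets the literal wording too, so (e) does not let through every child under current treatment.

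**Step 2: comparison with the neighbouring criteria.**

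- (b) diarrhoea: recent exposure excludes, over 2 weeks.
- (c) fever: recent exposure excludes, over 1 week.
- Zinc: recent exposure excludes, over 2 months.
- (e) antibiotics: exposure 7 or more days old excludes, and recent exposure does not.

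Only (e) runs in that direction.

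**Step 3: search for a correction.** No other part of the text shown restates the antibiotic criterion. The screening form in Appendix 5a (items 1 to 19) records current illness and previous immunisation but has no antibiotic item. This does not show that antibiotic history goes unrecorded. The selection section refers history-taking to Appendix 4a-4c, which is not available, and the form numbering jumps from item 40 in Appendix 5b to item 63 in Appendix 5c, so items 41 to 62 are not visible either.

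**Step 4: who gets through.** Of the children treated 0 to 6 days before enrolment, (b) removes those with diarrhoea in the past 2 weeks and (c) removes those with fever in the past week. The requirements that recruits be healthy and be examined by a physician remove some more. The group left is children treated recently who had neither diarrhoea nor fever in those windows.

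**Step 5: link to the stool culture.** The protocol gives no reason for (e) and does not tie it to the culture. Item (e) is anchored to enrolment and the culture to 4 days before vaccination, and no general interval between the two is stated. In the zinc component, supplementation starts at least 10 days before the first dose. If enrolment precedes supplementation, it precedes the culture by at least 10 − 4 = 6 days, so antibiotics taken before enrolment would be at least 6 days old at culture. Elsewhere the gap could be shorter. The effect on the screen is therefore possible, but its size is unknown.

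**The case against.** The strongest reply is that the intent is plain. Surrounded by look-back windows, (e) reads as loose English for treatment in the week or so before enrolment, and field staff are unlikely to reject a child for a course taken months ago while accepting one treated yesterday. This is probably right about intent. It makes the matter a wording fault to correct, not evidence of misconduct. It does not make the written rule correct, and even the charitable reading leaves the length of the window open, since a minimum of 7 days is not a defined period.

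Four stronger inferences are tempting, and the documents do not support them:

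- **That every recently treated child is admitted.** Items (b) and (c), the healthy-child requirement and the physician's examination act independently of (e). It is accurate only to say that such children are not excluded by (e).
- **That the stool screen is defeated.** No rate of antibiotic use or carriage is given, and nothing in the protocol states that antibiotics affect the culture. The most that can be said is that the screen may be weakened.
- **That the comparisons are biased.** Eligibility applies equally to all arms within a component, and the contrasts (dissolving fluid, breast milk, zinc) are made within components. Different populations between components would affect how results are described and carried forward, but would not by themselves bias any contrast.
- **That antibiotic history is not collected.** Appendix 5a also lacks items for chronic gastrointestinal disorder and prior zinc, so it is clearly not the only eligibility record, and other history pages are not visible.

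**Conclusion.** The point holds as a fault in the wording of an operative eligibility criterion. Read literally, (e) excludes antibiotic treatment 7 or more days before enrolment without limit and does not exclude treatment 0 to 6 days before. This is contrary to the form of the other three time-limited criteria, and nothing visible corrects it.

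The rule governs all 1140 planned children, but the number it would misclassify cannot be computed. The consequence for the stool screen rests on the assumption that recent antibiotics can suppress a positive culture, and is limited to recently treated children whom (b), (c) and the clinical examination do not catch. No error rate, power figure, sample size or endpoint changes. A reader might infer that the wrong children were enrolled. The text shows only that the rule as written would select them if followed literally. The correction should be made because it is cheap and the rule is applied to every child.

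**What to change.** The sponsor should reconcile (e) with the neighbouring criteria: confirm which period was intended, then restate it as a look-back before enrolment in the same form as (b), (c) and the zinc rule, with a defined length. The length is for the sponsor to decide. If one purpose of the criterion is to protect the stool culture, the text should say so and say whether the period runs back from enrolment or from the culture.

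The sponsor should also check that the history forms record antibiotic use and its date. If they do not, one item on the screening form in Appendix 5a would be enough.

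The cost is one sentence in the eligibility list and at most one line on a form, with no additional children, visits or procedures.
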